Medical and Psychiatric Evaluation: Once written informed consent has been obtained, the diagnosis will be confirmed by a Structured Clinical Interview for DSM IV (SCID). A detailed medical and psychiatric history, physical examination (including vital signs, height, and weight), an electrocardiogram, and laboratory assessments (standard screening blood tests: CBC with differential and platelet count, electrolytes, creatinine, BUN, liver enzymes, T4, calcium, phosphate, TSH, and magnesium levels) will be performed. In addition, a full lipid profile, fasting glucose and insulin levels will be obtained. A pregnancy test will be done in all premenopausal women. A routine urinalysis and drug screen will be done as part of the screening process.

Subjects will be administered the PANSS and motor side effects scales (AIMS, Barnes akathisia scale, Simpson Angus scale). IQ will be measured at screening using the Wechsler Test of Adult Reading (WTAR). Subjects will also be asked to provide an informant who can be contacted to collect clinical and safety information relevant to the outcome measures on each visit. This could be a clinician or a family member/friend who sees the patient at least on a weekly basis.

Study Design: In this 2 period cross over design, subjects will be randomized in a 1:1 ratio to receive either: **Order 1**: CBD (Period 1) followed by placebo (Period 2) or **Order 2**: Placebo (Period 1) followed by CBD (Period 2) under double-blind conditions. The 2 study periods will be separated by a washout of at least 2 weeks. During each period subjects will receive study medications (CBD [total 800mg/day] or placebo) for a period of 4 weeks. This dose is within the dose range of doses that have been shown to be effective and safe. Randomization to the order of medication assignment will be stratified by baseline PANSS scores.

Study Visits:

Subjects will have the following visits during each period except for Visit I (screening), which will occur only at the beginning of their participation in the study:

Visit I: Screening (At least two visits: Visit Ia and Visit Ib.)

Visit II: Baseline: Will initiate treatment with study drug following baseline assessments.

(Visits III, IV, V: Weekly clinical evaluation and study medication refill)

Visit III: (Week 1)

Visit IV: (Week 2)

Visit V: (Week 3)

Visit VI: (Week 4): End of treatment period visit

Visit VII: Safety Follow up at week 5.

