- 1. Positive and Negative Syndrome Scale (PANSS) (Visits I-VI): The PANSS includes 3 scales and 30 items: 7 items that make up the Positive Scale (eg, delusions, conceptual disorganization, hallucinatory behavior); 7 items that make up the Negative Scale (eg, blunted affect, emotional withdrawal, poor rapport, passive/apathetic social withdrawal); and 16 items that make up the General Psychopathology Scale (eg, somatic concern, anxiety, guilt feelings, mannerisms and posturing, motor retardation, uncooperativeness, disorientation, poor impulse control, preoccupation). Individual items are scored with values ranging from 1 to 7.
- 2. Personal and Social Performance Scale (PSP) (Visits I-VI): The PSP scale is a validated clinician-related scale that measures personal and social functioning in the domains of: socially useful activities (eg, work and study), personal and social relationships, self-care, disturbing and aggressive behaviors. Information from the subject and the informant will be utilized in determining the rating. The interview with the informant may be conducted by phone once the initial in-person interview has occurred and informed consent has been obtained.
- 3. Clinical Global Impression (CGI) (Visits I-VI):
 - **a.** Clinical Global Impression of Severity (CGI-S): The CGI-S consists of a single 7-point rating score of illness severity. Raters select one response based on the following question, "Considering your total clinical experience with this particular population, how mentally ill is your patient at this time?" Scores are: 1, Normal, not

- ill at all; 2, Borderline mentally ill; 3, Mildly ill; 4, Moderately ill; 5, Markedly ill; 6, Severely ill; or 7, Among the most severely ill subjects.
- b. Clinical Global Impression of Improvement (CGI-I): The CGI-I consists of a single 7-point rating score total improvement, regardless of whether or not the change it is due entirely to drug treatment. Raters select one response based on the following question, "Compared to your patient's condition at the beginning of treatment, how much has your patient changed?" Scores are: 1, Very much improved; 2, Much improved; 3, Minimally improved; 4, No change; 5, Minimally worse; 6, Much worse; or 7, Very much worse. For the CGI-I Scale, the subject's condition at the Day 1 (Baseline) visit will be the criterion for judging improvement at subsequent visits.

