DSMB: A Data Safety Monitoring Board is being assembled for this study. Unblinded safety data will be provided to the committee for monitoring purposes, in a meeting that will be held approximately every 6 months. DSMB reports will be provided to the HIC.

11. Statistical Considerations:

General Strategy:

All outcomes will be summarized descriptively and assessed for normality prior to analysis using normal probability plots and Kolmogorov test statistics. Transformations or nonparametric analyses will be performed as necessary. All tests will be two-sided and considered statistically significant at alpha=.05. Post-hoc comparisons will be performed as appropriate and significance levels for secondary analyses will be adjusted for multiple tests using the Bonferroni correction. All analyses will be performed using SAS, version 9.3 (SAS Institute Inc., Cary, NC).

Linear mixed models will be used assess symptom improvement as measured by the PANSS (primary hypothesis) and CGI. In these models group (CBD vs. placebo) and time (see study time points) will be modeled as within-subjects factor. Oder effects will also be tested. Least squares means and standard errors will be calculated in the mixed model and plotted to interpret significant effect. A significant group by time interaction explained by reduced symptoms over time due to CBD treatment will be supportive of our hypothesis. In the above models, the best fitting variance-covariance structure will be selected based on information criteria. The mixed effects approach is advantageous in that it is unaffected by randomly missing data and allows greater flexibility in modeling the correlation structure of repeated measures data [31]. Similar mixed models as described above will be employed to evaluate secondary outcomes (e.g., PAOFI, EEG parameters).

Power Analysis:

We will recruit 36 subjects and randomly assign 18 to receive either CBD followed by placebo (order 1) or placebo followed by CBD (order 2). Based on a within-subjects design and a two-tailed alpha=0.05, 36 subjects will provide 80% power to detect moderate treatment effects as small as d'=0.49. This compares favorably with the effects (d=0.7) observed by Leweke in their study comparing CBD to amisulpiride in schizophrenia patients.

SECTION VI: RESEARCH INVOLVING DRUGS, BIOLOGICS, RADIOTRACERS, PLACEBOS AND DEVICES

If this section (or one of its parts, A or B) is not applicable, state N/A and delete the rest of the section.

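### Randomisation to order is stratified by baseline PANSS, but the stratum is not in the analysis model, which leaves the order test conservative

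*Combined protocol and SAP*

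**What the plan says.** Section V, Study Design, describes the allocation: "In this 2 period cross over design, subjects will be randomized in a 1:1 ratio to receive either" of two sequences, labelled Order 1 (CBD, then placebo) and Order 2 (the reverse). It then says: "Randomization to the order of medication assignment will be stratified by baseline PANSS scores". It gives no cut-point and no number of strata.

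Section V, item 11 (General Strategy), sets out the linear mixed models for PANSS and CGI: "In these models group (CBD vs. placebo) and time (see study time points) will be modeled as within-subjects factor", followed by "Oder effects will also be tested". The criterion for success is: "A significant group by time interaction explained by reduced symptoms over time due to CBD treatment will be supportive of our hypothesis". The stratum is not named, and no baseline covariate is named.

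PANSS is rated at Visits I to VI (Outcome measures, item 1). Visit II is the pre-dose visit of each period: "Visit II: Baseline: Will initiate treatment with study drug following baseline assessments". The Power Analysis has 36 subjects, 18 per order, and claims 80% power for d'=0.49.

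**The concern.** When allocation is restricted on a prognostic factor, the analysis should contain that factor. Otherwise the standard error of any between-subject comparison is estimated as if allocation had been unrestricted, and it comes out too large. Study Design uses order as the name of the sequence, so a test of order compares different people and is exposed to this.

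At stake is how a null order result is read. In a two-period crossover, a non-significant order effect is usually taken as a sign that the sequence did not matter. If the test rejects far less often than its nominal 5% even by chance, that reading is too comfortable.

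**Working it through.** **1. The plan's own figure.** For a paired t-test with N = 36 and d' = 0.49, the noncentrality is 0.49 × √36 = 2.94. With 35 df and a critical value of 2.030, power is 0.816. The stated 80% reproduces.

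**2. The primary contrast.** The stratum is constant within a subject, so it cancels from a CBD-placebo comparison made within that subject. A generalised least squares calculation used ten visits (Visits II to VI in both periods) and correlation 0.5 / 0.7 / 0.8. The standard error of group by week 4 was 0.236 / 0.183 / 0.149 PANSS SD, identical with and without the stratum. In simulation with one value per period, power was about 0.82 either way.

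**3. The order contrast.** These inputs are assumptions, because the documents give no PANSS SD, correlation or cut-point:
- equal correlation ρ between any two PANSS ratings of a subject, with results in PANSS SD units;
- a stratum formed by a median split of Period 1 baseline, with 9 subjects per order in each half.

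The formulas, for a subject mean over m ratings, are:
- Variance of the mean: v = ρ + (1 − ρ)/m.
- Standard error of order without the stratum: √(v × (1/18 + 1/18)) = √(v/9).
- A median split captures 2/π = 0.637 of the variance of a normal baseline. With c the covariance between the subject mean and baseline, the standard error with the stratum is √((v − 0.637c²)/9).
- After stratified allocation the estimate varies with the smaller standard error, while the unadjusted test uses the larger. It therefore rejects when |Z| > 1.96 × (larger/smaller), which gives the approximate true type I error.

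Two outcome summaries bracket the answer. In A there is one on-treatment value per period (m = 2, c = ρ). In B all ten visits enter, with the Period 1 baseline among them (m = 10, c = v).

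| Summary | ρ | SE without | SE with | Reduction | Type I, formula | Type I, simulated |
|---|---|---|---|---|---|---|
| A | 0.5 | 0.289 | 0.256 | 11% | 2.7% | 3.3% |
| A | 0.7 | 0.307 | 0.245 | 20% | 1.4% | 1.3% |
| A | 0.8 | 0.316 | 0.234 | 26% | 0.8% | 0.8% |
| B | 0.5 | 0.247 | 0.199 | 19% | 1.5% | 1.6% |
| B | 0.7 | 0.285 | 0.208 | 27% | 0.7% | 0.7% |
| B | 0.8 | 0.302 | 0.209 | 31% | 0.5% | 0.5% |

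Worked line (B, ρ = 0.7): v = 0.7 + 0.3/10 = 0.73 and √(0.73/9) = 0.285. The stratum removes 0.637 × 0.73² = 0.339, leaving 0.391, and √(0.391/9) = 0.208. The threshold is 1.96 × 0.285/0.208 ≈ 2.68, so the type I error is 0.7%.

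With the stratum in the model, simulated type I error returned to about 5% in every row.

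**4. Baseline as a covariate instead.** Taking Period 1 baseline out of the response and using it as a covariate also sharpens the order test. But it raises the standard error of group by week 4 from 0.236 / 0.183 / 0.149 to 0.301 / 0.233 / 0.190. That is 0.301/0.236 ≈ 1.27, about 27% wider for the primary test.

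**The case against.** Several objections are sound and limit the point.

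- **Baseline PANSS is probably in the model already.** A reader might infer that the analysis ignores baseline altogether. The documents do not support that. Time runs over the study time points, PANSS is rated at Visit II, and success is a reduction over time. The natural reading is that Visit II PANSS is a response, though the General Strategy does not say so outright.
- **The primary result does not depend on this.** A reader might infer that the treatment estimate loses precision or that 36 subjects are too few. Step 2 shows neither. Nor does loss after Period 1 change it: with 20% or 30% lost (assumed, since no dropout rate is given), adding the stratum altered the standard error of group by week 4 by 0.0%.
- **The order test is not declared to be a carryover test.** A reader might infer that the plan's one safeguard against carryover fails. The General Strategy mentions neither carryover nor any decision tied to the order result. Study Design provides a washout of at least two weeks, and the Period 2 baseline visit allows residual effects to be examined directly.
- **The General Strategy is brief and may not list every term.** This is fair, but it does name the model's factors, the stratum is not among them, and nothing elsewhere in the document supplies it.
- **A conservative test makes no excess false claims.** That is true. For a check whose reassuring outcome is non-significance, however, conservatism errs in the unhelpful direction.

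**Conclusion.** The point holds as a minor one, confined to the order test. The factor used to restrict randomisation is left out of the analysis. As a result, the 18 versus 18 order comparison runs at a true type I error of roughly 0.5% to 3% instead of 5%, depending on the outcome summary, and its standard error is larger than it need be. Including the stratum lowers that standard error by about 11% to 31%.

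These sizes rest on a median split, equal correlations of 0.5 to 0.8 and complete data. Other cut-points or more strata would change them. They describe PANSS; the effect on CGI-S depends on how closely it follows PANSS, which the documents do not give. The group-by-time contrast, the sample size and the stated power stand.

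**What to change.** Add the PANSS randomisation stratum as a fixed between-subject effect in the PANSS and CGI-S mixed models, and test order in the model that contains it. State the cut-points and number of strata in Study Design. State in the General Strategy that Visit II PANSS of each period stays in the model as a response at a time point. Do not move Period 1 baseline from response to covariate while group by time is the primary test, because that widens its standard error.

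The cost is about one between-subject degree of freedom per added stratum level and a few sentences of text. No new data are needed.

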- **a. Psychiatric evaluation:** Subjects will undergo a Structured Clinical Interview for DSM-IV conducted by a research assistant and a psychiatric and medical evaluation during screening. The diagnostic interviews may cover issues, which are stressful to a person, for example, questions regarding the experience of paranoid thoughts or social isolation. Thus, they may experience some distress during these interviews.
- **b.** Loss of confidentiality: Participation in research may involve a loss of privacy and confidentiality. Therefore, extensive measures are in place to protect the confidentiality of subjects. (See below.)
- **c. Study assessments:** During the baseline and follow-up assessments, study participants may become tired or frustrated. If this occurs, they will be encouraged to take breaks. It is also possible that some individuals may experience discomfort during the interviews, when they are asked to talk about their psychiatric symptoms. Subjects may feel bored, tired, exhausted, discouraged or distressed by the questionnaires or EEG testing.
- **d. CBD administration:** CBD is a naturally occurring component of cannabis that has been used recreationally and for medicinal purposes by large populations. As mentioned above, studies have shown good tolerance of cannabidiol even in high doses with relatively few side effects and no known severe events. Sedation and/or lightheadedness are likely to be the most common reported adverse reaction. Patient will be assessed weekly for the development of side effects.

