- e. Worsening of psychosis: Participation in this study may be associated with worsening of psychosis especially in those individuals who are not on any other antipsychotics. Subjects will be evaluated on a weekly basis in face-to-face meeting with study staff. Psychotic symptoms, mood symptoms and suicidality will be assessed at each of these meetings. Further, subjects will be contacted approximately 5 times per week using CAROMA for the confirmation of compliance. During each of these visits, subjects will be asked if they have noticed any worsening of symptoms or any new side effects. If subjects report that they do notice a worsening of symptoms or side effects, this will be evaluated by an investigator on the team and subject will be asked to come into the clinic to be evaluated if clinically indicated. Subjects are well aware that in case of significant worsening of symptoms/ emergence of SI/HI, they may be escorted to the ER or admitted to an inpatient unit.
- **f. Risk of blood draws: B**lood will be drawn weekly during the study to monitor medication levels as well as safety labs. There are usually no serious medical problems with blood drawing, but there may be pain at the venipuncture site or bruising or infection may occur.
- **g. Risks of EEG:** EEG is a non-invasive assessment. There are minimal risks associated with EEG/ERP recording. Traditionally, scalp abrasion has been used to improve

signal impedance at the electrode site. The EEG/ERP system used in this laboratory is a high-impedance system and does not require scalp abrasion to obtain clean recording. A conductive gel is applied, which can be easily washed out of the subject's hair with warm water. A shower facility for hair washing and sterile linens are available in the laboratory. Electrode caps and sensors will be washed and sterilized between subjects to minimize the risk of transmitting infection.

Potential benefits: Subjects will receive no direct benefit from this study. Potential benefits may include improvement in psychotic and cognitive symptoms, decreased negative symptoms, avoidance of potential side effects from usual anti-psychotic medications themselves or from dose increases of such medications. Overall, the development of novel anti-psychotics will provide benefit to the schizophrenia population as a whole.

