that they do notice a worsening of symptoms or side effects, this will be evaluated by an investigator on the team and subjects will be asked to come into the clinic to be evaluated if clinically indicated. Subjects are well aware that in case of significant worsening of symptoms/ emergence of SI/HI, they may be escorted to the ER or admitted to an inpatient unit.

Risks of Blood Draws: Due to the risks associated with phlebotomy procedures, subjects who have donated blood within eight weeks to the present study will be excluded. Subjects will be told that they should not give blood for at least eight weeks.

Risks of EEG: The risk of irritation during EEG set up will be minimized through careful application of electrodes and appropriate cleansing of the skin by trained technicians.

- 10. **Data and Safety Monitoring Plan:** Include an appropriate Data and Safety Monitoring Plan (DSMP) based on the investigator's risk assessment stated below. (Note: the HIC will make the final determination of the risk to subjects.) For more information, see the Instructions, page 24.
 - **a.** What is the investigator's assessment of the overall risk level for subjects participating in this study? Moderate risk
 - **b.** If children are involved, what is the investigator's assessment of the overall risk level for the children participating in this study? No children will be enrolled.
 - c. Copy, paste, and then tailor an appropriate Data and Safety Monitoring Plan from http://www.yale.edu/hrpp/forms-templates/biomedical.html for
 - i. Minimal risk
 - ii. Greater than minimal/moderate risk
 - iii. High risk

SAFETY: Subjects will be closely monitored for worsening of symptoms or side effects. They will be provided with a 24 hour access to study personnel to discuss any concerns. Subjects will be given a wallet card indicating they are taking experimental medication and directions for how to determine what they are taking in case of an emergency.

Adverse events will be reported to the HIC and any appropriate funding and regulatory agencies. The investigator will apprise fellow investigators and key study personnel of all serious and unanticipated adverse events that occur during the conduct of this research project. Adverse events will be graded as per HIC policy.

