Data safety and monitoring plan: This is a moderate risk study, and no serious adverse events are expected. If any should occur, however, the following grading system will be used to assess the seriousness of the adverse events:

- 0 No adverse event or within normal limits
- 1 Mild adverse event
- 2 Moderate adverse event
- 3 Severe adverse event resulting in hospitalization or prolongation of existing hospitalization, a persistent or significant disability/incapacity, or a congenital anomaly/birth defect.

- 4 Life-threatening or disabling adverse event
- 5 Fatal adverse event

Serious unanticipated adverse events will be reported immediately to the VA Connecticut Healthcare System, Yale University School of Medicine, California Pacific Medical Center institutional review boards and any appropriate funding and regulatory agencies. Serious anticipated adverse events will be reported immediately to the institutional review boards and others whenever their magnitude or frequency exceeds expectations.

The principal investigator will evaluate all adverse events and determine whether the adverse event affects the risk/benefit ratio of the study and whether modifications to the protocol or consent form are required. A summary of the adverse events will be reported to the institutional review boards periodically or, at minimum, when reapproval of the protocol is sought. The summary will include number of subjects enrolled and a summary of graded adverse events to date. All adverse events will be graded using the following grading system:

Attribution	Grade	1	Grade	2	Grade	3	Grade	4	Grade	5
	UNA	ATP	UN	ATP	UN	ATP	UN	ATP	UN	ATP
	TP		ATP		ATP		ATP		ATP	
Unrelated										
Unlikely										
Possible										
Probable										
Definite										
Totals										
Total Subjects Enrolled to Date										

The principal investigator will be responsible for monitoring the data and conducting performance of safety reviews at regular intervals, as indicated above. The principal investigator will conduct a data and safety review at least quarterly and at any time a serious adverse event occurs. During the review process the principal investigator will evaluate whether the study should continue unchanged, require modification, continue or close to enrollment.

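### The adverse event scale mixes severity with seriousness, so some events fit two grades and one kind of severe event fits none

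*Combined protocol and SAP*

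**What the plan says.** The scale is in Section V, item 10, under the paragraph headed Data safety and monitoring plan. Its stated purpose is that "the following grading system will be used to assess the seriousness of the adverse events". Grade 0 means no event, and Grade 5 is a fatal one. The grades between are:

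- Grade 1: "Mild adverse event"
- Grade 2: "Moderate adverse event"
- Grade 3: "Severe adverse event resulting in hospitalization or prolongation of existing hospitalization, a persistent or significant disability/incapacity, or a congenital anomaly/birth defect"
- Grade 4, given with its number: "4 Life-threatening or disabling adverse event"

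The same item then requires every adverse event, not only serious ones, to be entered in a table of attribution by Grades 1 to 5. The review boards receive the graded counts periodically, and at least when re-approval is sought. Immediate reporting depends on whether an event is serious, not on a grade number. The SAFETY paragraph just before the scale says: "Adverse events will be graded as per HIC policy". That policy is not reproduced.

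Two statements under Section V, item 8 (Risks) show which events to expect. Under CBD administration: "Sedation and/or lightheadedness are likely to be the most common reported adverse reaction". Under Worsening of psychosis, subjects who worsen significantly are told that "they may be escorted to the ER or admitted to an inpatient unit".

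**The concern.** Severity is how intense an event is. Seriousness is what the event led to. An event can be severe without being serious, and moderate yet serious. This scale puts both on one axis: the lower grades use intensity alone, Grade 3 joins an intensity word to a list of outcomes, and the top grades are outcomes. Such a scale can be expected to overlap where two outcomes share a word, and to leave gaps where intensity and outcome part company.

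What is at stake is the safety record. The graded table is what the review boards see, and the scale is the only tool the plan states for judging seriousness, on which immediate reporting depends. Good tolerability is also a main part of the case that the Background section makes for CBD. If two raters can grade the same event differently without either breaking a rule, the counts by grade are hard to interpret.

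**Working it through.** No formula or stated figure is involved. The check takes kinds of event and asks which grade definitions each one meets as worded.

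| Kind of event | Grade(s) that fit | Result |
|---|---|---|
| Severe, admitted, no disability, not life-threatening | 3 | clear |
| Severe, birth defect only | 3 | clear |
| Life-threatening, not admitted, no disability | 4 | clear |
| Fatal, not admitted | 5 | clear |
| Severe with lasting or significant disability, admitted or not | 3 and 4 | overlap |
| Life-threatening, admitted | 3 and 4 | overlap |
| Severe, none of the Grade 3 outcomes, not life-threatening, disabling or fatal | none | gap |
| Moderate, admitted | 2 by intensity, 3 by outcome | conflict |

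Four of these eight kinds have one clear grade and four do not (8 − 4 = 4). This counts kinds of event, not how often each will occur; the documents give no rate for any of them.

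**Overlap.** Disability appears in 2 of the 5 event grades. Nothing separates the disability of Grade 3 from the disabling event of Grade 4, and no rule says to assign the higher grade when two apply.

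**Gap.** Grade 3 is the only grade labelled severe, and its wording ties that label to a list of outcomes. The outcomes are joined by *or*, so admission is not required: disability or a birth defect is enough. Grades 4 and 5 do not need admission either. The gap is therefore limited to severe events that meet none of the outcomes in Grades 3 to 5.

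**Applied to the risks the plan names.** Take two subjects with equally severe worsening of psychosis, neither in danger of dying nor disabled. One is seen in the emergency room and goes home; the other is admitted. The first meets no grade as worded and the second is Grade 3. If the worsening is moderate in both, the first is Grade 2, while the second is Grade 2 or Grade 3 depending on whether the rater follows intensity or outcome. In each pair the difference comes from disposition, not from intensity. Severe sedation in an outpatient has the same difficulty: it has no grade unless the rater regards it as a significant incapacity or it meets another listed outcome.

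**The case against.** The best case on the other side has five parts.

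1. **The direction of any error is unknown.** A reader might infer that severe events outside the listed outcomes slide down to Grade 2, so that CBD looks better tolerated than it is. The plan states no such default. A rater could equally choose Grade 3, the only grade that carries the word. The Background and Risks sections also report mild somnolence and no known severe events, so the documents give no basis for estimating how many severe events might be affected. This objection stands: the claim is inconsistency, not understatement.

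2. **Admission is not the only way into Grade 3.** It would be wrong to say that severe sedation cannot reach Grade 3 without it, because the disability and incapacity wording may apply. This also stands, and it keeps the gap narrow.

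3. **There may be only one grading system.** The SAFETY paragraph cites HIC policy, and the form tells investigators to adapt an institutional template, so the scale may be that policy written out. One might infer that two systems compete, but the policy cannot be seen and the documents do not show a conflict. What remains is that the two statements are not linked.

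4. **Other safeguards exist.** The UKU side effects scale is given weekly, and the motor scales, PANSS and CGI are rated at visits whatever the subject's disposition. A monitoring board receives unblinded safety data about every six months and reports to the HIC. Immediate reporting is keyed to the word serious, and no hypothesis or planned analysis uses the grades. All this limits the harm. None of it is said to correct the graded table sent to the review boards.

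5. **A smaller repair would do.** A boundary for disability, a rule that the highest grade applies, and a place for severe events without listed outcomes would remove the ambiguities. That is true as far as assigning a grade goes. But a severe event without admission and a moderate event with admission could then both be Grade 3, and the table could not tell them apart.

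**Conclusion.** The point holds as a defect in a stated rule. Disability appears in two grades without a boundary, a life-threatening event with admission fits two grades, a moderate event with admission can be read two ways, and a severe event with none of the listed outcomes fits no grade. The graded summary to the review boards can therefore be inconsistent, in an unknown direction, and for worsening of psychosis the grade can depend on admission rather than intensity.

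The number of events affected cannot be derived from the documents, and no rate is assumed here. The conclusion rests on reading the definitions as written and on the absence from the plan of any tie rule or separate seriousness field. The HIC policy might supply one, which cannot be checked. Efficacy analyses, power and sample size are untouched. The change should be made because it is cheap and concerns safety reporting; the trial's validity does not depend on it.

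**What to change.** In Section V, item 10, replace the single scale with two fields for every adverse event:

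- **Severity:** mild, moderate or severe, judged by intensity alone.
- **Seriousness:** a yes/no flag carrying the outcome criteria now spread over Grades 3 to 5 (hospitalization, disability, birth defect, life-threatening, fatal), with disability listed once.

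Lay out the summary table for the review boards by these two fields. Reword the SAFETY paragraph and the Data safety and monitoring plan paragraph so that both point to the same system; if the HIC policy is that system, say so.

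The cost is one extra column on the adverse event form and in the summary table, plus re-coding of any events already recorded.
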